20.8. Quality Audits

Medtronic reserves the right to conduct quality audits at the investigational centers in order to verify adherence to external regulations as well as internal policies and procedures, to assess adequacy and effectiveness of clinical policies and procedures, to assure compliance with critical study document requirements, to confirm integrity and accuracy of clinical study data and to protect the safety, rights and welfare of study subjects.

These audits are done in addition to the regular monitoring visits.

Regulatory bodies may also perform inspections at participating investigation sites. Any regulatory authority inspection announcements shall be forwarded immediately to the sponsor contact person.

The investigator and/or institution shall permit Medtronic and regulatory bodies direct access to source data and documents, taking into account any restrictions due to local law, to perform clinical study-related monitoring, audits, EC/IRB review, and regulatory inspections.

20.9. Investigational Center Disqualification

Medtronic and/or the IRB/EC retain the right to disqualify an investigational center and remove all study materials at any time. Specific instances, which may precipitate investigational center disqualification, include but are not limited to:

- Unsatisfactory subject enrollment with regard to quality and quantity.
- Persistent non-compliance to protocol procedures on the part of an Investigator/investigational center. Inaccurate, incomplete, and/or untimely data recording on a recurrent basis.
- The incidence and/or severity of adverse experiences in this or other studies indicating a potential health hazard caused by the device.
- Unsatisfactory accountability of investigational devices.

A written statement fully documenting the reasons for such a termination will be provided to Medtronic, the Institutional Review Board (IRB) or Ethics Committee (EC) and other regulatory authorities, as required.

20.10. Protocol Deviations

A deviation is any instance(s) of failure to follow, intentionally or unintentionally, the requirements of the protocol. It is expected that the investigator will conduct this clinical trial in compliance with the protocol and all applicable regulations governing the conduct of clinical research involving human subjects. Failure to do so could result in one or all of the following:

- Observation in the monitoring report
- Deviation to document the event
- Corrective action plan
- Investigational center disqualification
- Notification to the regulatory authorities / IRB/EC depending on the severity of the deviation and reporting requirements

The investigator is responsible for protecting the safety and welfare of the clinical research subjects.

20.11. Compliance with Protocol

The investigator or person designated by the investigator will document and explain any deviation from the approved protocol that occurs during the course of the clinical trial. The date and reason for each deviation will be documented. (21 CFR 812.140 Records for US/ ISO14155:2011 9.6g for EMEA)

The investigator should not implement any deviation from, or changes of, the protocol without agreement by the sponsor and prior review and documented approval/favorable opinion from the IRB/EC of an amendment, except where necessary to eliminate an immediate hazard(s) to trial subjects, or when the change(s) involves only logistical or administrative aspects of the trial (e.g., change of monitor(s), change of telephone number(s)).

The investigator may implement a deviation from, or a change in, the protocol to eliminate an immediate hazard(s) to trial subjects without prior IRB/EC approval/favorable opinion. As soon as possible, the implemented deviation or change, the reasons for it, and, if appropriate, the proposed protocol amendment(s) should be submitted:

- To the IRB/EC for review and approval/favorable opinion
- To the sponsor for agreement and, if required
- To the regulatory authority or authorities

Except in an emergency, prior approval by the sponsor, FDA/local regulatory authority in EMEA and IRB/EC is required for changes in or deviations from a plan, and if these changes or deviations may affect the scientific soundness of the plan or the rights, safety, or welfare of human subjects. (21 CFR 812.35(a) for US / ISO14155:2011 4.5.4 b)) .

In any emergency situation the investigator shall exercise his/her judgment to safeguard the subject's interest. The investigator shall report a deviation as soon as possible to Medtronic and the reviewing IRB/EC, according to IRB/EC reporting guidelines, as applicable. Medtronic will inform the regulatory authorities, if required.

Emergency deviations must be reported to the sponsor and IRB/EC within 5 days.

The following examples are deviations that could impact subject safety, affect the integrity of study data and/or affect subject's willingness to participate in the study. These deviations are significant and require immediate sponsor notification upon investigator awareness:

- Failure to obtain informed consent, i.e., there is no documentation of informed consent
- Informed consent obtained after initiation of study procedures
- Enrollment of a subject who did not meet all inclusion/exclusion criteria
- Performing study procedure not approved by the IRB/EC
- Failure to report serious adverse event to the IRB/EC and sponsor
- Investigational study device dispensed without obtaining informed consent

Medtronic is responsible for analyzing deviations, assessing their significance, and identifying any additional corrective and/or preventive actions (e.g. amend the CIP, additional training, terminate the study, etc.). Repetitive or serious investigator compliance issues may result in the need to initiate a corrective action plan, and in some cases freeze enrolment or ultimately terminate the investigator's participation in the clinical study (see section 20.10).

The investigator will propose any appropriate modification(s) of the Clinical Investigation Plan or investigational device/product or investigational device/product use. Medtronic will review this proposal and decide whether the modification(s) will be implemented.

Medtronic will submit any significant amendment to the Clinical Investigation Plan, including a justification for this amendment, to the appropriate regulatory authorities and to the investigators to obtain approval from their IRB/EC. The investigator will only implement the amendment after approval of the IRB/EC, regulatory authority and sponsor. Administrative amendments to the Clinical Investigation Plan will be submitted to the IRB/EC for notification. Furthermore investigators shall sign any approved amendment for agreement.

21. Device Deficiencies and Troubleshooting

The Medtronic 24-Hour HL will be consulted for device troubleshooting (e.g. assistance is needed by subject to operate their device(s)). When subjects call the Helpline (HL), they are instructed to notify the HL operator that they are currently participating in a clinical study. All device deficiencies that are reported to the HL will be documented by the HL staff. Medtronic will review all device deficiencies and determine whether the deficiency requires reporting to regulatory agencies. The sponsor will ensure timely Device Deficiency reporting to meet regulatory requirements.

Note: For commercially available devices, device deficiency reporting will be documented per study and relevant regulatory requirements

The investigational center will be provided with a copy of all HL calls for their subjects. The HL calls should be reviewed for investigational center staff awareness and for the possibility of an AE. If an AE is detected the investigational center staff will also complete an AE eCRF.

All device deficiencies reported directly to the investigational center staff by a subject should either be reported to the HL by the subject or investigational center staff. Any device deficiency the investigational center may have should be reported to the HL. A device deficiency is any communication that alleges inadequacy of a medical device with respect to its identity, quality, durability, reliability, safety, or performance. NOTE: Device deficiencies include malfunctions, use errors, and inadequate labeling. **(Adapted from ISO14155:2011)**

All device returns will follow the 24-Hour HL procedures. To return a study device as part of a device deficiency, the investigational center and or subject are to call the 24-Hour HL.

It is the responsibility of the Investigator to follow the center's IRB/EC and local regulatory authority reporting requirements.

For EMEA region only:

Device deficiencies that did not lead to an Adverse Event but could have led to an SADE

- a) if either suitable action had not been taken,
- b) if intervention had not been made, or
- c) if circumstances had been less fortunate, require immediate reporting to the sponsor and to IRB/EC and regulatory authority per local reporting requirements ISO14155:2011 (section 6.4.2).

22. Study Endpoints

22.1. Descriptive Endpoints

22.1.1. During the Home Period

- The mean change in A1C will be presented from baseline to end of study
- Change of Total Daily Dose (TDD) of insulin from baseline to end of study
- Change of weight from baseline to end of study
- Time spent in Auto Mode versus time spent in Manual Mode

- Time in different range (% of SG): SG < 50, 54, 60, 70 mg/dL, 70 mg/dL ≤ SG ≤ 180 mg/dL, SG > 180, 250 mg/dL, 350 mg/dL
- Number of Events, AUC and Time in the hyperglycemic range: sensor glucose (SG) > 180, 250, 350 mg/dL
- Number of Events, AUC and Time in the hypoglycemic range: SG < 50, 54, 60, and 70 mg/dL

22.1.2. During the Run-In Period

Low Management Suspend before Low Evaluation:

- Success rate of prevention of hypoglycemia (i.e. 1 - percent of *Low Management Suspend before Low* experiments that have 2 or more consecutive reference glucose values of ≤ 65 mg/dL)
- *Low Management Suspend before Low* Performance
- Sensor performance

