A total of up to 200 subjects (age 2-13) will be enrolled at up to 15 investigational centers (14 in the US, 1 in the Europe, Middle East and Africa (EMEA) region) in order to reach 120 subjects who will complete the HCL study. The run-in period will primarily be used to allow subjects to become familiar with the new study devices. During the run-in period, subjects will be using the Study Pump (670G) with the Sensor Augmented Pump function only activated (i.e. SmartGuard Low Management features OFF and Auto Mode OFF). At the end of the CGM run-in period at Run-in Visit 4, subjects 7-13 years of age will be asked to undergo 12 hours (maximum) of *Low Management Suspend before Low* frequent sample testing on the first day of sensor wear. Testing will begin during the day and extend for an overnight stay at the clinic. Subjects 2-6 years of age will not undergo frequent sample testing procedures at this visit. (Please see section 11.4 for further details).

Manual Mode: Run-in Pump Settings **before** frequent Sample testing, i.e.: *Low Management Suspend before Low*

- High and Low Setup limits and alert(s) will be set at investigator discretion
 - Low Setup Limit may not be set lower than 65mg/dL
 - For subjects 2-6 years of age, Low Setup Limit should be set at 80mg/dL and no lower than 70mg/dL
- SmartGuard –Low Management must be OFF during this period
- SmartGuard – Auto Mode must be OFF during this period

Manual Mode: Run-in Settings Pump **during** frequent Sample testing, i.e. *Low Management Suspend before Low*:

- Low Setup limit for subjects 7-13 years must be set at 65 mg/dL
- Subjects 2-6 years of age will not participate in frequent sample testing, but will still complete Visit 4.
- Alert before low should be ON
- Resume basal alert should be ON

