11.4.5. Repeat Rules for *Low management Suspend before Low* In-Clinic Procedures

Subjects may repeat in-clinic procedures once on a different day; however, the total amount of blood drawn must not exceed 2 mL/kg of body weight during any 24 hour period and 4 ml/kg over a 1 month period for the entire study. Criteria to allow the repeat of an in-clinic visit are as follows:

- Subject arrives for in-clinic visit with blood ketone concentration greater than 1.5 mmol/L
- Concurrent failure of both the primary and back-up YSI instruments during frequent sample testing
- Investigational center staff enters the incorrect Low Limit setting
- If a sensor fails prior to the start of YSI or before 8 hours of YSI, the in-clinic procedures will be re-scheduled
- When *Low management Suspend before Low* is turned ON and triggers prior to exercise, the in-clinic procedures will be re-scheduled
- An insulin pump infusion set catheter occlusion is suspected (i.e. occlusion alarm)
- Subjects 7-13 years: Less than 8 hours of YSI data collected and subject never reached 65 mg/dL or less (2 contiguous YSI samples)
- Less than 4 hours of observation from the time that *Low management Suspend before Low* activates

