11.4.6. Subject Stopping Rules for *Low management Suspend before Low* In-Clinic Procedures

- Prior to starting in-clinic testing, ketone level is greater than 1.5 mmol/L.
- Subjects 7-13 years: Twelve hours have passed since the start of exercise without *Low management Suspend before Low* activation.
- If *Low management Suspend before Low* is activated, observation with YSI frequent sample testing will include the Suspend period (30 minutes minimum to 2 hours maximum) and insulin resumption period (approximately 4 hours from time insulin resumes). This may include insulin re-suspension during this period. Maximum observation with YSI frequent sample testing should be performed no longer than 12 hours for subjects 7-13 years of age. If *Low management Suspend before Low* does not trigger then observation with YSI frequent sample testing will be performed for no longer than 12 hours (Subjects 7-13 years)..
- Sensor fails prior to the start of YSI or before 8 hours of YSI (Subjects 7-13 years).
- An insulin pump infusion set catheter occlusion is suspected (i.e., occlusion alarm).
- YSI glucose is greater than 500 mg/dL regardless of ketone levels.
- Ketones are greater than or equal to 3 mmol/L, regardless of blood glucose.
- Suspected DKA
- Severe hypoglycemia
- Persistent elevation of ketone greater than or equal to 1.5 mmol/L after hydration

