24.3.3. Sample Size Justification

24.3.3.1. Sample Size for Primary Endpoint

The overall mean change in A1C from baseline to the end of study will be estimated and compared by a simple superiority paired test and a significance level of 0.025 (one-sided).

The hypothesis is mathematically expressed as:

Ho: $\mu \geq 0\%$

Ha: $\mu < 0\%$

Where μ is the mean of % of change in A1C (3-month - baseline). The null hypothesis will be rejected if the one-sided 97.5% upper confidence limit of the mean change in A1C is less than 0%.

Assuming the mean of change in A1C from baseline to the 3-month follow-up visit is zero, the standard deviation of change in A1C is 1.1%, SAS power and sample size calculator shows that a total of 80 subjects (7-13 years old) will provide 90% power to detect the difference of 0.4% and with one-sided type I error of 0.025.

A minimum of 95 subjects will be enrolled to account for subject attrition

24.3.3.2. Sample Size for Secondary Endpoint: % of Time in Euglycemia (70 – 180 mg/dL)

The overall mean change in % of time in euglycemia (70-180 mg/dL) from baseline to the end of study will be estimated and compared by a simple superiority paired test and a significance level of 0.025 (one-sided).

Ho: $\mu \leq 0\%$

Ha: $\mu > 0\%$

Where μ is the mean of change in % of time in euglycemia (3-month - baseline). The null hypothesis will be rejected if the one-sided 97.5% lower confidence limit of the mean change in % of time in euglycemia is greater than 0%.

Assuming the mean of change in time in euglycemia (%) from baseline to the 3-month follow-up visit is zero, the standard deviation of change in percentage time in euglycemia is 11.0%, SAS power and sample size calculator shows that a total of 80 subjects (7-13 years old) will provide 90% power to detect the difference of 4.0% and with one-sided type I error of 0.025.

A minimum of 95 subjects will be enrolled to account for subject attrition

24.3.3.3. Sample Size for Secondary Endpoint: % of Time in Hyperglycemia (> 180 mg/dL)

The overall mean change in % of time in hyperglycemia (> 180 mg/dL) from baseline to the end of study will be estimated and compared by a simple superiority paired test and a significance level of 0.025 (one-sided).

The hypothesis is mathematically expressed as:

Ho: $\mu \geq 0\%$

Ha: $\mu < 0\%$

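### The Suspend before Low 'prevention' rate counts a full-length session with no activation and no low as a success, so it can only be biased upward

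*Protocol*

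**What the plan says.** The synopsis, Section 22.1.2 and Section 24.2 give the same definition: "Success rate of prevention of hypoglycemia (i.e. 1 - percent of" Suspend before Low "experiments that have 2 or more consecutive reference glucose values of ≤ 65 mg/dL". The definition mentions neither activation of the feature nor a fall in glucose towards the limit. The protocol does not define what counts as an experiment.

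During the test the pump limit equals the failure threshold: "Low Setup limit for subjects 7-13 years must be set at 65 mg/dL" (synopsis and Section 4).

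Section 11.4.6 expects that some sessions will not trigger the feature. One stopping rule reads "Twelve hours have passed since the start of exercise without" activation. Another says that if the feature "does not trigger then observation with YSI frequent sample testing will be performed for no longer than 12 hours".

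Section 11.4.5 lists the grounds for repeating a session. The one for sessions that never went low is "Less than 8 hours of YSI data collected and subject never reached 65 mg/dL or less (2 contiguous YSI samples").

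**The concern.** A rate labelled as prevention of hypoglycemia will be read as a measure of what the device does. A session in which glucose stayed well above the limit and insulin was never suspended says nothing about that, yet the definition scores it as a success. The weaker the exercise challenge, the higher the reported rate, whatever the device does.

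The synopsis names the feature in the study purpose, and this is the only measure of prevention for which the protocol gives a formula. The neighbouring bullet on the feature's performance is not specified. The study is single-arm, so no control sessions show how many children would have stayed above 65 mg/dL without the feature.

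**Working it through.** The protocol states no target, expected value or sample size for this rate, so there is no figure to reproduce. The check has two parts: what the wording does with each kind of session, and how far the rate can move.

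**Scoring of sessions as written**

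| Feature activated | Two consecutive values ≤ 65 mg/dL | Scored as |
|---|---|---|
| yes | no | success |
| yes | yes | failure |
| no | yes | failure |
| no | no | success |

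The last row is the problem.

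**Can a session in the last row stand as completed?** Section 11.4.6 lets a session without activation run to 12 hours. The repeat grounds in Section 11.4.5 do not reach it:
- The never-low ground needs less than 8 hours of YSI data.
- The ground on less than 4 hours of observation runs only from an activation.
- The others (ketones on arrival, failure of both YSI instruments, wrong limit entered, early sensor failure, triggering before exercise, suspected occlusion) describe faults that a quiet, full-length session does not have.

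Nothing in the protocol takes such a session out of the denominator.

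**Size.** Let a be the share of sessions that activate and p the share of activated sessions without a qualifying low. Neither is in the protocol; both are assumed below. Assume first that non-activated sessions have no lows.

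- Rate as written: a·p + (1 − a) = 1 − a(1 − p)
- Rate among activated sessions: p
- Difference: (1 − a)(1 − p), which is never negative

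| | a = 0.9 | a = 0.7 | a = 0.5 |
|---|---|---|---|
| p = 80%: rate as written | 82% | 86% | 90% |
| p = 60%: rate as written | 64% | 72% | 80% |

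The shift is 2, 6 and 10 points in the first row and 4, 12 and 20 points in the second.

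In counts, take 80 sessions. This number is borrowed for scale only from the A1C sample size ("a total of 80 subjects (7-13 years old) will provide 90% power", Section 24.3.3.1).
- 64 activated, 13 with a low: 1 − 13/80 = 83.8% as written; 1 − 13/64 = 79.7% among activated.
- 48 activated, 14 with a low: 1 − 14/80 = 82.5%; 1 − 14/48 = 70.8%.
- 32 activated, 16 with a low: 1 − 16/80 = 80.0%; 1 − 16/32 = 50.0%.
- All 80 activated: the two rates are equal.
- None activated and no lows: 100% as written; the rate among activated sessions is undefined.

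**If some non-activated sessions do go low.** Let q be that share. Failures as a share of all sessions are F = a(1 − p) + (1 − a)q. Sessions with activation or a low are D = a + (1 − a)q. The rate as written is 1 − F and the rate among sessions with activation or a low is 1 − F/D. The difference is F(1 − D)/D, which again cannot be negative. With q = 0 it reduces to (1 − a)(1 − p). The direction therefore does not depend on the first assumption; only the simple form of the size does.

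**The case against.** Several points on the other side stand.

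- 'Experiment' is undefined. A statistical analysis plan, not available here, or the separate in-clinic procedure guidelines could restrict it to sessions with activation. But the protocol states the formula itself, three times, without that restriction, and its in-clinic rules let sessions without activation run to completion. The point is about a stated rule, not a detail left for later.
- A reader might infer that every session is counted. The documents do not support that: Section 11.4.5 allows several kinds of failed or short session to be repeated, and does not say whether the first attempt counts. The defect concerns full-length sessions with neither activation nor a low.
- A reader might also infer that the study's conclusion on the feature is compromised. It is not. The synopsis purpose is to show safety, Section 3 does not name the feature, and the Section 11.4.7 criteria are no UADE, no device-related SAE and no DKA. The rate has no hypothesis or threshold, and Section 24.3.3 does not size the study for it.
- The unspecified performance bullet could hold activation counts. It may, but that would not change the formula for the rate.
- Restricting the denominator does not yield a clean prevention rate. The feature acts on a predicted low, so an activated session without a low may never have been heading low, and there are no control sessions to tell. This is right. It limits what either rate can claim, but does not justify counting as prevention a session in which the feature did nothing.
- The all-session figure is a legitimate estimate of the share of sessions free of hypoglycemia. That also stands; what is wrong is its label.

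**Conclusion.** The point holds in a limited form. On the protocol's wording, a full-length session with no activation and no qualifying low is scored as prevented hypoglycemia, and this can only raise the rate. If non-activated sessions have no lows, the upward shift is (1 − a)(1 − p). It is zero when every session activates and runs from 2 to 20 points over the tabulated range of assumed inputs. The documents give neither a nor p, so no particular size can be claimed, and a large inflation should not be inferred.

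The consequence is confined to how a descriptive figure will be read. No test and no safety success criterion changes. The definition is still worth correcting, because it fixes a flattering figure under a label that claims more than it measures, and the correction is cheap.

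**What to change.** In the synopsis, Section 22.1.2 and Section 24.2:

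1. Define an experiment as a completed session, and state how a session that is repeated under Section 11.4.5 is counted.
2. Compute the prevention rate among sessions in which the feature activated plus sessions with two consecutive reference values at or below 65 mg/dL without activation. Count the latter as failures, so that missed detections are not hidden.
3. Report sessions with neither as a separate count labelled 'no activation, no low'. This label is safer than 'not challenged', since glucose may have come close to the limit in some of them.
4. Keep the all-session figure as a second line, labelled as the share of sessions free of hypoglycemia.
5. Note that without control sessions neither rate proves prevention.

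The cost is a wording change and an extra table row, with no new data or procedure. The downside is a smaller denominator, hence less precision, and a somewhat less favourable rate.
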